Appendix 10 Formulae for Measurements

- MELD Score = $(9.57 * \ln[\text{creatinine}]) + (3.78 * \ln[\text{Bilirubin}]) + (11.20 * \ln[\text{INR}]) + 6.43$
- ELF assay combines hyaluronic acid, procollagen 3 amino terminal peptide, and tissue inhibitor of metalloproteinase 1. An algorithm is used to evaluate each of these markers by immunoassay, to create an ELF Score.
- FIB4 score = $(\text{age} [\text{years}] \times \text{AST level} [\text{U/L}]) / (\text{platelet count} [\times 10^9/\text{L}] \times \text{square root of ALT} [\text{U/L}])$
- APRI score = $([\text{AST divided by AST Upper Limit of Normal}] / \text{platelet count} [\times 10^9/\text{L}]) \times 100$
- NAFLD Fibrosis Score = $-1.675 + 0.037 \times \text{age} (\text{years}) + 0.094 \times \text{BMI} (\text{kg}/\text{m}^2) + 1.13 \times \text{fasting glucose/diabetes (yes = 1, no = 0)} + 0.99 \times \text{AST/ALT ratio} - 0.013 \times \text{platelet count} - 0.66 \times \text{albumin} (\text{g/dL})$

[figure not shown]
Method of BMI Calculation:

- Use actual height and weight collected on the same day. Whenever possible, body weight should be measured using the same scale throughout the study.
- To calculate BMI:
 - Convert weight pounds to kg (kg = pounds/2.2)
 - Convert height inches to centimeters (cm = inches \times 2.54)
 - $\text{BMI} = (\text{weight in kg}) / (\text{height in cm}/100)^2$
 - Round to 1 decimal place (if 0.05 or greater, round up)

Appendix 11 Decision Tree for Long-Term Immunogenicity Follow-Up Visits After the Week 52/PTFU Visit

Participants who discontinue study medication prior to Week 48 are expected to complete an ET Visit and to remain in the study and continue to have immunogenicity monitored according to the Schedule of Events in Section 1.

Participants who discontinue study participation will be offered immunogenicity follow-up visits, as per the diagram. All participants will have immunogenicity samples collected at 6 months after the Week 52/PTFU Visit. Additional immunogenicity follow-up visits may occur approximately 9, 12, and 14 months, if applicable, (visit window \pm 14 days) (1 month is defined as 4 calendar weeks) after the last completed study visit.

FU = Follow-Up; IMG = Immunogenicity (anti-drug and anti-FGF21 antibodies); Mo = month (defined as 4 calendar weeks)

^a All participants will have samples collected for immunogenicity at 6 months (\pm 14 days) after the Week 52/PTFU Visit. Samples collected from participants may not be analyzed if: 1) participant is not on active drug, 2) participant is negative for anti-drug and/or anti-FGF21 antibody titers at the Week 52/PTFU Visit, or 3) participant has evidence of stable or decreasing antibody titers for 2 visits prior to the 6-month posttreatment visit

^b Additional assessments include: basic metabolic panel, hemoglobin A1c [REDACTED]

## 1.0 Introduction

The statistical analysis plan (SAP) describes the statistical methods to be used during the reporting and analyses of data collected under Bristol-Myers Squibb (BMS) Protocol MB130-069.

The Statistical Analysis Plan outlines the following:

- Study design
- Study objectives
- Endpoints
- Analysis populations
- Statistical methods
- Conventions and definitions

This SAP should be read in conjunction with the study protocol (version 4.0, 30 January 2020) and electronic case report (eCRF) [REDACTED] according to Page 1 of this document. Any further changes to the protocol or eCRF may necessitate updates to this SAP. Changes following approval of the first version SAP will be tracked in the SAP Change Log and a final version of the updated SAP will be approved prior to database lock.

## 2.0 Study Design

### 2.1 Overall Study Design

This is a multicenter, double-blind, placebo-controlled, randomized, parallel-group study to demonstrate the efficacy and safety of BMS-986036 in the treatment of participants with NASH and compensated cirrhosis.

The study will consist of 4 periods:

- A Screening Period of up to 8 weeks in duration (this period may be extended to total of up to 12 weeks upon discussion with the medical monitor)
- A 48-week, Double-Blind Treatment Period, during which the participants will receive blinded study treatment (BMS-986036 10 mg, 20 mg, 40 mg once weekly (QW) or matching placebo QW)
- A 4-week Post-Treatment Follow-up [PTFU] Period
- A Follow-Up Period of up to 14 months (1 month is defined as 4 calendar weeks) after the Week 52/PTFU Visit for the collection of an additional dual-energy X-ray absorptiometry (DXA) assessment (in all participants), samples for potential immunogenicity testing (in all participants) as well as plasma and serum for biomarkers (in all participants) at 6 months ( $\pm$  14 days) Post Week 52/PTFU. Subsequent visits at 9, 12, and 14 months after Week 52 or PTFU will be performed in participants for whom Long-Term Immunogenicity Follow-Up Visits are required.

At the end of the Screening Period, participants meeting all inclusion and no exclusion criteria will enter the Double-Blind Treatment Period.

Participants will be enrolled and randomized via interactive response technology (IRT) to receive BMS-986036 10 mg QW, BMS-986036 20 mg QW, BMS-986036 40 mg QW or matching placebo QW in a 1:1:1:1 ratio. A liver biopsy will be performed during the Screening Period (if historical biopsy meeting protocol requirements is not available) and at Week 48 in all participants.

Arm 1: BMS-986036 (10 mg QW)  
Arm 2: BMS-986036 (20 mg QW)  
Arm 3: BMS-986036 (40 mg QW)  
Arm 4: Placebo

The protocol was planned to randomize approximately 100 participants to 1 of 4 treatment groups (approximately 25 participants per group). Protocol amendment v4.0 reflects that upon close of enrollment approximately 155 participants were randomized to treatment (approximately 38 participants).

Sponsor: Bristol-Myers Squibb

Protocol No.: MB130-069

per group). The increased number of randomized participants occurred following: 1) unexpectedly high enrollment rate in the final month of the enrollment period; 2) several participants who had initially been enrolled into FALCON 1 (MB130-068) were determined (based on central pathology biopsy results) to qualify for FALCON 2 (MB130-069) during the period between the closure of enrollment and completion of randomization; and 3) an unexpected decrease in the actual screen failure rate for subjects entered in the final month of enrollment.

Based on the unmet medical need for patients, the benefit/risk assessment discussed in Protocol [Section 6.3](#), and the strict safety monitoring of all participants, the potential clinical benefit outweighs the risks for those who have chosen to participate in this study. No additional revisions are required to the statistical considerations due to the increased number of randomized participants.

Randomized participants will receive their assigned double-blind study treatment for a total of 48 weekly doses. The treatment will be administered by subcutaneous (SC) injection of 2 prefilled syringes of study treatment in the abdomen according to their assigned treatment arm. During the Double-Blind Treatment Period, participants will be evaluated for safety and efficacy every 4 weeks ( $\pm 5$  days) through Week 24 and every 8 weeks ( $\pm 5$  days) after Week 24 through Week 48.

A schematic of the study design is displayed in [Figure 1](#) (Screening to Week 52/Post-Treatment Follow-up [PTFU]) and [Figure 2](#) (follow-up visits after the Week 52/PTFU Visit).

Sponsor: Bristol-Myers Squibb

Protocol No.: MB130-069

### Figure 1. Study Design Schematic – Screening to Week 52/PTFU

[figure not shown]
[figure not shown]

Figure 2. Study Schematic – Bone Mineral Density and Immunogenicity Follow-Up Visits After the Week 52/PTFU Visit (visit windows ± 14 days) (1 month is defined as 4 calendar weeks)

Sponsor: Bristol-Myers Squibb

Protocol No.: MB130-069

## 2.2 Sample Size Considerations

The primary efficacy endpoint is the proportion of participants with a  $\geq 1$ -stage improvement in fibrosis (as defined by NASH Clinical Research Network (CRN) Fibrosis Score) without worsening of NASH (as defined by the NAFLD Activity Score) at Week 48, as determined by liver biopsy.

It is planned to randomize approximately 100 participants to 1 of the 4 treatment groups (approximately 25 participants per group), BMS-986036 10 mg QW, BMS-986036 20 mg QW, BMS-986036 40 mg QW or matching placebo QW in a 1:1:1:1 ratio. The final sample size was approximately 155 participants.

## 2.3 Randomization

Randomization will be conducted in the following manner:

Participants will be stratified at randomization by country (Non-Japan versus Japan). Participants in countries other than Japan will be stratified at randomization according to Type 2 Diabetes Mellitus (T2DM) status (yes versus no). Japanese participants will not be further stratified.

- Eligible participants will be randomized by the IRT using a prespecified schedule in a double-blind manner to 10 mg BMS-986036, 20 mg BMS-986036, 40 mg BMS-986036, or placebo arms in a 1:1:1:1 ratio based on the stratification factors specified in [Section 2.1](#).
- The IRT will provide study treatment kit numbers that contain the appropriate study treatment (BMS-986036 or placebo) for dispensation to that participant.

At subsequent study visits, the investigator or designee will access the IRT to receive the corresponding kit numbers assigned to the participant for the purpose of dispensing study treatment.

## 2.4 Unblinding Information

The Data Monitoring Committee (DMC) provides oversight of safety considerations throughout the study. A separate unblinded team, comprised of an unblinded Independent Reporting Statistician (IRS) and unblinded programmer(s), will produce output for the DMC using masked treatments. Treatment decodes may only be requested by the DMC Chair and will be provided by the IRS. Data summaries and listings will be transmitted via a secure portal by the IRS to only the DMC members. Additional details regarding the DMC process and unblinding are provided in the DMC charter.

Sponsor and designee personnel may be unblinded once all participants have completed the Week 52/PTFU Visit and all data have been collected through that time point to facilitate analyses. Designated sponsor staff may be unblinded (obtain the randomization codes) prior to database lock to facilitate the bioanalytical analysis of PK samples and immunogenicity. A bioanalytical scientist in the sponsor Bioanalytical Sciences department (or a designee in the external central bioanalytical laboratory) will be unblinded to (may obtain) the randomized treatment assignments in order to minimize unnecessary bioanalytical analysis of samples.

## 2.5 Clarification from Protocol

- The protocol specifies that study medication is defined as any investigational treatment(s), marketed product(s), placebo or medical device intended to be administered to a study participant according to the study randomization or treatment allocation, and study treatment includes both investigational [medicinal] product and non-investigational [medicinal] product. For the purposes of the calculations contained in this SAP, study treatment will include only doses of BMS-986036 or placebo.
- Impact due to COVID-19 on study visits is not described in the protocol, a summary table of patients with delayed or missed visits, and the listing of missed visits will be presented.

Sponsor: Bristol-Myers Squibb

Protocol No.: MB130-069

### 3.0 Study Objectives

#### 3.1 Primary Efficacy Objective

The primary efficacy objective of this study is:

- To evaluate the efficacy of BMS-986036 in adults with NASH and compensated cirrhosis based on improvement in fibrosis without worsening of NASH as determined by liver biopsy at Week 48.

For this protocol, improvement in fibrosis is defined as a decrease of fibrosis by  $\geq 1$  point, as determined by the NASH CRN Fibrosis Score. Worsening of NASH is defined as an increase of the NAFLD Activity Score (NAS) by  $\geq 1$  point.

#### 3.2 Secondary Efficacy Objectives

The secondary efficacy objectives of this study are:

- To evaluate the impact of BMS-986036 on improvement of fibrosis as determined by liver biopsy at Week 48
- To evaluate the impact of BMS-986036 on improvement in fibrosis without worsening of NASH or improvement of NASH as determined by liver biopsy at Week 48
- To evaluate the impact of BMS-986036 on resolution of NASH, as determined by liver biopsy at Week 48
- To evaluate the impact of BMS-986036 on improvement of NASH, as determined by liver biopsy at Week 48
- To evaluate the impact of BMS-986036 on collagen proportionate area (CPA) as determined by liver biopsy at Week 48

#### 3.3 Safety Objectives

The safety objectives of this study are to demonstrate the safety of BMS-986036 in adults with NASH and compensated cirrhosis throughout the course of the study, including bone mineral density and immunogenicity.

#### 3.4 Pharmacokinetic Objectives

- To determine trough concentrations of BMS-986036 in all participants

#### 3.5 Exploratory Objectives

To explore the impact of BMS-986036 administration on the following parameters:

- Quantitative assessments of fibrosis and fat on biopsy
- Nonalcoholic fatty liver disease (NAFLD) Activity Score (NAS)
- Digital pathology assessment of NASH
- Hepatic fat fraction by magnetic resonance imaging-proton density fat fraction (MRI-PDFF)
- Noninvasive measures of fibrosis and/or cirrhosis
- Metabolic assessments
- Child-Pugh Turcotte score
- Model for End-Stage Liver Disease (MELD) score
- Liver-related clinical outcome events
- Patient-reported outcomes
- Exploratory biomarkers

Sponsor: Bristol-Myers Squibb

Protocol No.: MB130-069

## 4.0 Endpoints

### 4.1 Primary Efficacy Endpoint

The primary efficacy endpoint of this study is the proportion of participants who achieve a  $\geq 1$ -stage improvement in fibrosis (as defined by NASH CRN Fibrosis Score) without worsening of NASH (as defined by the NAFLD Activity Score) at Week 48 as determined by liver biopsy.

Improvement in fibrosis is defined as a decrease of fibrosis by  $\geq 1$  point, as determined by the NASH CRN Fibrosis Score. Worsening of NASH is defined as an increase of the NAFLD Activity Score (NAS) by  $\geq 1$  point (details on scoring is provided in the protocol [Section 8.5.1.1](#)).

### 4.2 Secondary Efficacy Endpoints

The secondary efficacy endpoints are the proportion of participants with the following:

- Ishak Score  $>=1$  stage improvement at Week 48
- NASH CRN Fibrosis Score  $\geq 1$ -stage improvement (as defined by NASH CRN Fibrosis Score) in fibrosis without worsening of NASH or NASH improvement (reduction of NAS by  $\geq 2$  points with contribution from  $> 1$  NAS component) at Week 48
- $>= 1$ -stage improvement (as defined by NASH CRN Fibrosis Score) in fibrosis
- Any CPA decrease at Week 48
- NASH resolution (NAS component of ballooning = 0 and inflammation = 0-1) at Week 48
- NASH improvement (reduction of NAS by  $\geq 2$  points with contribution from  $> 1$  NAS component) at Week 48

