There is considerable intra- and inter-individual variation of hepatopathologist assessment of fibrosis stage on liver biopsy. Assessment of CPA is a method by which the amount (percentage) of collagen in stained tissue Sections is analyzed using morphometric image analysis. This allows for a quantitative assessment of fibrosis. Percentage of fat in stained tissue Sections is also analyzed using morphometric image analysis. These morphometric assessments will be performed by a blinded Central Pathologist. Additional details on these morphometric assessments are in the Central Pathology Manual.

Assessment of NASH and Fibrosis Using Digital Pathology

Liver biopsy samples will be evaluated using digital pathology, which may include automated techniques.²⁹

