9. STATISTICAL CONSIDERATIONS

9.1 Sample Size Determination

The primary efficacy endpoint is the proportion of participants with a \geq 1-stage improvement in fibrosis (as defined by NASH CRN Fibrosis Score) without worsening of NASH (as defined by the NAFLD Activity Score) at Week 48, as determined by liver biopsy.

It is planned to randomize approximately 100 participants to 1 of the 4 treatment groups (approximately 25 participants per group), BMS-986036 10 mg QW, BMS-986036 20 mg QW, BMS-986036 40 mg QW or matching placebo QW in a 1:1:1:1 ratio.

A Cochran-Armitage trend test of proportions, with an estimated response rate of 15% for the primary endpoint for placebo and response rates for BMS-986036 10 mg QW, BMS-986036 20 mg QW, and BMS-986036 40 mg QW of 20%, 30%, and 40%, respectively, would provide at least 70% power at a 1-sided $\alpha = 0.05$ (based on original sample size estimate of approximately 100 participants). The final sample size was approximately 155 participants (see Section 6.2).

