9.4.1.2 Secondary Efficacy Endpoints

Secondary efficacy endpoints are as follows:

- Proportion of participants with Ishak Score improvement at Week 48
- Proportion of participants who achieve a ≥ 1 -stage improvement (as defined by NASH CRN Fibrosis Score) in fibrosis without worsening of NASH or NASH improvement (reduction of NAFLD Activity Score by ≥ 2 points with contribution from > 1 NAS component) at Week 48 as determined by liver biopsy
- Proportion of participants who achieve a ≥ 1 -stage improvement (as defined by NASH CRN Fibrosis Score) in fibrosis
- Proportion of participants with a decrease in CPA at Week 48
- Proportion of participants with NASH resolution (NAS component of ballooning = 0 and inflammation = 0-1) at Week 48
- Proportion of participants with NASH improvement (reduction of NAFLD Activity Score by ≥ 2 points with contribution from > 1 NAS component) at Week 48

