#### 4.5 Exploratory Endpoints

Exploratory endpoints include the following:

- Quantitative measurements of fibrosis and fat on biopsy
  - Assessment of NASH CRN Fibrosis Score at Week 48
    - Proportion of participants with  $\geq 1$  stage improvement
    - Proportion of participants with  $\geq 2$  stage improvement
    - Proportion of participants with  $\geq 2$  stage improvement without worsening of NASH
    - Changes in Fibrosis (as expressed by Shift from baseline)
    - Proportion of participants with  $\geq 1$  stage improvement, no change, or worsening
  - Assessment of Ishak Fibrosis Score at Week 48
    - Proportion of participants with  $\geq 2$  stage improvement
    - Changes in Fibrosis (as expressed by Shift from baseline)
    - Proportion of participants with  $\geq 1$  stage improvement, no change, or worsening
  - Assessment of qFibrosis using digital pathology at Week 48
    - Absolute, percent change, and change from baseline
  - Assessment of CPA at Week 48
    - Proportion of participants with any improvement
    - Absolute, percent change, and change from baseline
  - Assessment of fat and alpha-SMA in stained tissue by morphometry at Week 48
    - Absolute, percent change, and change from baseline
- Assessment of NAS score at Week 48
  - Changes in NAS (as expressed by shift from baseline, for each individual NAS components (Steatosis, inflammation, Ballooning) as well as Total score)
  - Proportion of participants with improvement, no change, or worsening in NAS Total
- Hepatic fat fraction as measured using MRI-PDFF at Week 24 and Week 48
  - Absolute, percent change, and change from baseline
  - Proportion of subjects in each treatment group with  $\geq 30\%$  relative reduction,  $\geq 20\%$  relative reduction,  $\geq 10\%$  relative reduction, and  $\geq 5\%$  absolute reduction
- Noninvasive measures of fibrosis and/or cirrhosis
  - Liver stiffness as determined by Magnetic Resonance Elastography (MRE) at Week 24 and Week 48
    - Absolute, percent change, and change from baseline
    - Proportion of subjects in each treatment group with  $\geq 19\%$  or  $\geq 15\%$  reduction
  - Fibroscan elastography results at Week 48
    - Absolute, percent change, and change from baseline
    - Proportion of subjects in each treatment group with any decrease by time point

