#### 6.1.1 Primary Efficacy Analysis

The primary efficacy endpoint is the proportion of participants who achieve a  $\geq 1$ -stage improvement (as defined by NASH CRN Fibrosis Score) in fibrosis without worsening of NASH (as defined by NAFLD Activity Score) at Week 48, as determined by liver biopsy.

Improvement in fibrosis is defined as a decrease of fibrosis by  $\geq 1$  point, as determined by the NASH CRN Fibrosis Score. Worsening of NASH is defined as an increase of the NAFLD Activity Score (NAS) by  $\geq 1$  point.

Participants will be stratified at randomization by country (Non-Japan versus Japan). Participants in countries other than Japan will be stratified at randomization according to Type 2 Diabetes Mellitus (T2DM) status (yes versus no). Japanese participants will not be further stratified.

If lack of response in the strata prohibits analysis, the strata may be reduced to Japan/Non-Japan only or no stratification at all.

Sponsor: Bristol-Myers Squibb

Protocol No.: MB130-069

A Cochran-Armitage trend test of proportions at a one-sided 0.05 level of significance will be used to examine the linear trend among the proportions across treatment groups. The null hypothesis states that there is no association between treatment level and fibrosis stage improvement. The alternative hypothesis states that there is an association between treatment level and fibrosis stage improvement.

The proportion of participants with response will be summarized by strata as well as overall for each treatment group. Shift tables will be presented for the NAFLD Activity Score and NASH CRN Fibrosis Score. A bar chart of response/non-response in the primary endpoint will be provided.

All participants who prematurely discontinue from treatment without a biopsy at Week 48 (or ET, if applicable) or otherwise have a missing Week 48 (or ET, if applicable) biopsy result will be considered non-responders for the primary analysis of the primary efficacy endpoint.

All biopsy results will be included in the participant listings.

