#### 6.1.2 Secondary Efficacy Analyses

All secondary efficacy analyses will be conducted among the mITT population using the same methodology as the primary efficacy analysis. A completer analysis is not planned for secondary efficacy analyses.

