For continuous endpoints the analysis of covariance (ANCOVA) models will be used to explore changes from baseline that include fixed factors for the treatment group and the corresponding covariate for baseline value for the following:

- Quantitative measurements of fibrosis and fat on biopsy
  - Assessment of qFibrosis using digital pathology
  - Assessment of CPA
  - Assessment of fat and alpha-SMA by morphometry
- Hepatic fat fraction as measured using MRI-PDFF
- Noninvasive measures of fibrosis and/or cirrhosis
  - Liver stiffness as determined by MRE
  - Fibroscan elastography results
  - APRI, FIB-4, and NAFLD scores
- Exploratory biomarkers
  - Transaminases ALT and AST
  - PRO-C3

A repeated measures analysis will model changes from baseline for each of the exploratory endpoints separately for data collected at planned visits using restricted maximum likelihood estimations. The model will include treatment group, visit, baseline value, treatment \* visit and baseline stratification factors as fixed effects. An unstructured covariance matrix will be used to represent the correlation of the repeated measures within each subject. This model will be used to provide point estimates for the treatment differences, standard errors for the differences, and corresponding 2-sided 95% confidence intervals for mean change from baseline at each time point. Statistical inferences for comparing treatment groups will utilize Kenward-Rodgers Degrees of Freedom.

Other biomarkers will be descriptively summarized by time point and will include percent change from baseline in addition to change from baseline.

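### The secondary CPA endpoint keeps only the direction of change in a continuous fibrosis measure, while the more powerful baseline-adjusted analysis is left exploratory and without a dose-trend test

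*SAP*

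**What the plan says.** Protocol 9.4.1.2 lists the endpoint as "Proportion of participants with a decrease in CPA at Week 48". SAP 4.2 states it as "Any CPA decrease at Week 48". Neither sets a threshold. The objective behind it (Protocol 7.2, SAP 3.2) is the drug's impact on CPA.

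SAP 6.1.2 analyses all secondary endpoints in the mITT population "using the same methodology as the primary efficacy analysis", which is "A Cochran-Armitage trend test of proportions at a one-sided 0.05 level of significance" (SAP 6.1.1). SAP 6.4 confirms that participants with no Week 48 or ET biopsy count as non-responders on biopsy endpoints. SAP 6.1.2 plans no completer analysis for secondary endpoints.

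Protocol 8.5.1.1 explains why CPA is measured. Pathologists' staging varies within and between readers, and of the morphometric method it says "This allows for a quantitative assessment of fibrosis".

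The continuous form appears only among the exploratory endpoints: absolute value, change and percent change (SAP 4.5). SAP 6.4 says "For continuous endpoints the analysis of covariance (ANCOVA) models will be used to explore changes from baseline", with treatment group and baseline value as terms, and CPA is on its list. A repeated-measures model in the same section gives treatment differences with 95% confidence intervals. Neither model has a contrast for dose trend. The proportion with any CPA improvement is listed a second time in SAP 4.5 and 6.4.

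**The concern.** CPA is the only morphometric measure among the six secondary endpoints, and it is there because it is quantitative. Reducing it to the sign of its change makes a trivial fall equal to a large one. It also forgoes adjustment for baseline CPA and scores every missing biopsy as a failure. Under the plan, the only dose-trend test on CPA is the one on this binary response.

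What is at stake is whether the CPA objective can detect a moderate dose effect on collagen. Protocol 6.2.1 says that Phase 3 design and dose selection will rest on the totality of the results, so a weak answer here feeds into that decision.

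**Working it through.** **The plan's own figure.** Only the primary endpoint is powered. Protocol 9.1 says that response rates of 15, 20, 30 and 40% at 25 per arm "would provide at least 70% power at a 1-sided" 0.05. Let d be the centred scores (−1.5, −0.5, 0.5, 1.5), so Σd² = 5. Then:

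power = Φ[(nΣdp − 1.645√V0)/√V1], with V0 = p̄(1−p̄)·n·Σd² and V1 = nΣd²p(1−p).

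- nΣdp = 25 × 0.425 = 10.625
- V0 = 0.2625 × 0.7375 × 125 = 24.20
- V1 = 22.98
- power = Φ[(10.625 − 1.645 × 4.919)/4.794] = Φ(0.53) = 70%

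The stated figure reproduces, so the same formula is used for CPA.

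**Assumptions for CPA (none is in the documents).** Change is normal with SD 1. Placebo change is centred on zero. The fall at 40 mg is D standard deviations and falls linearly to zero across the arms. Baseline and Week 48 variances are equal, with correlation ρ = 0.5. Missing biopsies run from 0 to 15%, alike in all arms. There are 38 per arm (about 155 in total). The test is one-sided at 0.05.

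- Sign rule: p for arm j = Φ(Dj/3), j = 0 to 3, multiplied by (1 − missing fraction).
- Unadjusted change: power = Φ[√n·Σdδ/√5 − 1.645], where δ = Dj/3 and n counts observed biopsies.
- ANCOVA: as for unadjusted change, but with the first term divided by the residual SD √((1+ρ)/2) = √0.75 = 0.866.

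**Worked case, D = 0.5, none missing.**

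- Sign rule: p = 0.500, 0.566, 0.631, 0.691; nΣdp = 12.14; V0 = 45.71; V1 = 44.16. Power = Φ[(12.14 − 1.645 × 6.761)/6.645] = Φ(0.15) = 56%.
- Unadjusted change: √38 × 0.8333/2.236 = 2.297. Power = Φ(0.652) = 74%.
- ANCOVA: 2.297/0.866 = 2.653. Power = Φ(1.008) = 84%.

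Of the 28 points lost, 18 come from dichotomising and 10 from not adjusting for baseline.

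| D (SD) | Missing | Sign rule | Unadjusted change | ANCOVA | Loss v ANCOVA (points) |
|---|---|---|---|---|---|
| 0.2 | 0% | 18% | 23% | 28% | 10 |
| 0.4 | 0% | 42% | 58% | 68% | 26 |
| 0.5 | 0% | 56% | 74% | 84% | 28 |
| 0.6 | 0% | 69% | 87% | 94% | 25 |
| 1.0 | 0% | 97% | >99% | >99% | 3 |
| 0.2 | 15% | 15% | 21% | 25% | 10 |
| 0.4 | 15% | 33% | 52% | 62% | 29 |
| 0.5 | 15% | 44% | 68% | 79% | 35 |
| 0.6 | 15% | 55% | 82% | 90% | 35 |
| 1.0 | 15% | 87% | >99% | >99% | 13 |

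With none missing, dichotomising alone costs about 16 to 18 points at 0.4 to 0.6 SD. At D = 0.5, 15% missing lowers the sign rule by 12 points (56% to 44%) but ANCOVA by only 5 (84% to 79%). That is the cost of counting missing as failure.

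**Sensitivity.**

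- Simulation at D = 0.5 gives 55% v 83% with none missing and 45% v 78% with 15% missing, so the formulas may run a point or two high. Under no effect both tests reject about 5% of the time.
- With ρ = 0.7 the residual SD is √0.85 = 0.922, and the loss with none missing is about 22, 24 and 22 points at 0.4, 0.5 and 0.6 SD. With ρ = 0.3 and 10% missing it is 34 to 38 points (155 in total, effects shaped like the protocol's 15/20/30/40%).

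**Is the near-50% response rate the cause?** With zero median change, 50% of participants with a biopsy respond by chance, or 42.5% after 15% missing (0.5 × 0.85). Moving the cut shows that this is not what costs power. For D = 0.6 with none missing (155 in total, effects shaped as in the protocol), power is 71% at any decrease and 73% at a 0.25 SD cut (placebo rate 40%). It is 66% at 1 SD (placebo rate 16%) and 53% at 1.5 SD (placebo rate 7%). A cut near zero is close to the best single cut.

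**The case against.** The strongest reply is that the information is not lost. Continuous CPA change with a baseline covariate is already prespecified. No testing hierarchy or multiplicity adjustment applies (SAP 6.1.3), so relabelling it as secondary moves no alpha. All six secondary endpoints are proportions, the SAP follows the protocol faithfully, and CPA was never powered. This stands, and it limits the point to one of rank and of a missing trend contrast.

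The power comparison also bundles three things: dichotomising, baseline adjustment, and a different handling of missing biopsies. That is right, and the working separates them. Every CPA input is assumed. Losses are largest at moderate effects and small at either end, so no single figure describes the plan.

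A reader might infer that a 50 to 60% response in a treated arm would pass for benefit. The documents do not support that: there is a concurrent randomised placebo arm, and the test is a trend across arms. A reader might also infer that regression to the mean inflates the response rate. Entry is on the central reader's NASH CRN classification (Protocol 8.3.1), not on CPA, so the size of any such shift is speculative. Randomisation would spread it over all arms alike.

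**Conclusion.** The point holds as a matter of efficiency and rank. The secondary CPA test discards magnitude, while a better analysis sits in the exploratory list without a trend contrast. Under the stated assumptions (about 38 per arm, normal change, linear trend, correlation 0.5 to 0.7, 0 to 15% missing), the loss against ANCOVA is about 22 to 35 points for effects of 0.4 to 0.6 SD. It is about 10 points at 0.2 SD. At 1.0 SD and correlation 0.5 it is about 3 points with none missing and 13 with 15% missing.

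Two stronger readings fail. The test is not invalid, because its error rate is kept. And the near-50% chance response, itself an assumption of zero median change, does not cause the power loss. It only makes the proportion harder to interpret, and a stricter threshold would barely help power. The Fibroscan proportion uses a similar rule, "Proportion of subjects in each treatment group with any decrease by time point", but it is already exploratory beside its own ANCOVA, so nothing needs to change there.

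**What to change.** In SAP 4.2 and 6.1.2, make change from baseline in CPA at Week 48/ET the secondary CPA analysis. Use the SAP 6.4 ANCOVA (treatment, baseline CPA), and add a linear dose contrast at one-sided 0.05 and differences from placebo with confidence intervals. Keep the any-decrease proportion, with its non-responder rule and trend test, as supportive.

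Protocol 9.4.1.2 needs a matching documented change. Protocol 9.5.2.2 lets the SAP vary the secondary methods, but it does not say that the SAP may replace an endpoint. The change should be made before unblinding.

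The cost is wording plus one contrast, since the data and model are already planned. The downside is that ANCOVA uses only participants with a biopsy. Reporting the non-responder version alongside shows whether missing biopsies alter the conclusion.
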